16.3 Appendix 3: Specific Renal Alert Criteria and Actions and Event Follow-up

Criteria	Action required	
Serum cystatin C increase 25 – 49%	Consider causes and possible interventions	
compared to baseline	Follow up within 2-5 days	
Serum cystatin C increase ≥ 50%	Consider causes and possible interventions	
	Repeat assessment within 24-48h if possible	
	Consider drug interruption or discontinuation	
	Consider hospitalization and specialized treatment	
	Consider causes and possible interventions	
	Assess serum albumin & serum protein	
New onset dipstick proteinuria ≥ 1+	Repeat assessment to confirm	
	Consider drug interruption or discontinuation unless other causes are diagnosed and corrected	
.	Assess & document:	
New onset glycosuria on urine dipstick (unless related to treatment, diabetes)	Blood glucose (fasting)	
(unless related to treatment, diabetes)	Serum cystatin C	
	Assess & document:	
New hematuria on dipstick concomitant	Urine sediment microscopy	
	Assess serum cystatin C	
	 Exclude infection, trauma, bleeding from the distal urinary tract/bladder, menstruation 	
	Consider bleeding disorder	

Additional specialized assessments are available to assess renal function or renal pathology. (Note: In exceptional cases when a nephrologist considers a renal biopsy, it is strongly recommended to make specimen slides available for evaluation by Novartis to potentially identify project-wide patterns of nephrotoxicity.)

Whenever a renal event is identified, a detailed subject history and examination are indicated to identify, document and potentially eliminate risk factors that may have initiated or contributed to the event:

- Blood pressure assessment (after 5 min rest, with an appropriate cuff size)
- Signs and symptoms such as fever, headache, shortness of breath, back or abdominal pain, dysuria, hematuria, dependent or periorbital edema
- Changes in blood pressure, body weight, fluid intake, voiding pattern, or urine output
- Concomitant events or procedures such as trauma, surgical procedures, cardiac or hepatic failure, contrast media or other known nephrotoxin administration, or other potential causes of renal dysfunction, e.g., dehydration, hemorrhage, tumor lysis

Action Follow up		
Assess*, document and record in the Case Report Form (CRF) or via electronic data load. Review and record possible contributing factors to the renal event (co-medications, other co-morbid conditions) and additional	 Urine dipstick and sediment microscopy Blood pressure and body weight Serum cystatin C, electrolytes (sodium, potassium, phosphate, calcium), bicarbonate and uric acid 	
diagnostic procedures (MRI etc) in the CRF.	Urine output	
	• Event resolution: (serum cystatin C within 10% of baseline or protein-creatinine ratio within 50% of baseline)	
Monitor subject regularly (frequency at investigator's discretion) until:	or	
	• Event stabilization: serum cystatin C level with ±10% variability over last 6 months or protein- creatinine ratio stabilization at a new level with ±50% variability over last 6 months.	

Table 16-5Follow up of renal events

* Urine osmolality: in the absence of diuretics or chronic kidney disease this can be a very sensitive metric for integrated kidney function that requires excellent tubular function. A high urinary osmolality in the setting of an increase in CysC will point toward a "pre-renal" cause rather than tubular toxicity.

16.4 Appendix 4: Prohibited Co-Medication

Table 16-6 Narrow therapeutic index CYP substrates

Category	Drug Names
Narrow therapeutic index substrates of CYP2B6	None reported to date
Narrow therapeutic index substrates of CYP2C8	paclitaxel
Narrow therapeutic index substrates of CYP2C9	phenytoin, (S)-warfarin (also sensitive)
Narrow therapeutic index substrates of CYP2C19	(S)-mephenytoin (also sensitive)
Narrow therapeutic index substrates of CYP3A	abemaciclib, acalabrutinib, astemizole, cyclosporine, dihydroergotamine, entrectinib, ergotamine, pimozide, quinidine, sirolimus, tacrolimus, zanubrutinib

Table 16-7 Strong and moderate inhibitors of CYP3A

Category	Drug Names
Strong inhibitors of CYP3A	boceprevir, ceritinib, clarithromycin, cobicistat, conivaptan, danoprevir/ritonavir, elvitegravir/ritonavir, grapefruit juice, idelalisib, indinavir, indinavir/ritonavir, itraconazole, josamycin, ketoconazole, lopinavir/ritonavir, mibefradil, mifepristone, nefazodone, nelfinavir, ombitasvir/paritaprevir/dasabuvir/ritonavir (Viekira Pak), posaconazole, ribociclib, ritonavir, saquinavir, saquinavir/ritonavir, telaprevir, telithromycin, tipranavir/ritonavir, troleandomycin, tucatinib, voriconazole
Moderate inhibitors of CYP3A	ACT-178882, ACT-539313, aprepitant, amprenavir, atazanavir, atazanavir/ritonavir, casopitant, cimetidine, ciprofloxacin, crizotinib, darunavir, darunavir/ritonavir, diltiazem, dronedarone, duvelisib, erythromycin, faldaprevir, fedratinib, FK1706, fluconazole, grapefruit juice, GSK2647544, imatinib, isavuconazole, istradefylline, lefamulin, letermovir, Magnolia vine (Schisandra sphenanthera), netupitant, nilotinib, ravuconazole, tofisopam, verapamil, voxelotor

Table 16-8	Strong and moderate inducers of CYP3A
------------	---------------------------------------

Category	Drug Names
Strong inducers of CYP3A	apalutamide, avasimibe, carbamazepine, enzalutamide, ivosidenib, lumacaftor, mitotane, phenobarbital, phenytoin, rifampicin, rifapentine, St. John's wort (Hypericum perforatum)
Moderate inducers of CYP3A	asunaprevir / beclabuvir / daclatasvir, bosentan, cenobamate, dabrafenib, elagolix, efavirenz, etravirine, lesinurad, lersivirine, lopinavir, nafcillin, PF-06282999, phenobarbital, primidone, rifabutin, talviraline, telotristat ethyl, thioridazine, tipranavir/ritonavir

Table 16-9Substrates of MATE1/2

Category	Drug Names
Substrates of MATE 1/2	acyclovir, cephalexin, cimetidine, ganciclovir, fexofenadine, glycopyrronium, metformin, pindolol, pilsicainide, procainamide, ranitidine, topotecan, varenicline

16.5 Appendix 5: Permitted concomitant therapy requiring caution and/or action

Category	Drug Names
Sensitive substrates of CYP2B6	bupropion
Sensitive substrates of CYP2C8	daprodustat, repaglinide
Sensitive substrates of CYP2C9	benzbromarone, celecoxib, glimepiride, glipizide, ibuprofen, lornoxicam, meloxicam, piroxicam, tolbutamide
Sensitive substrates of CYP2C19	(R)-(-)-hexobarbital, clobazam, (R)-lansoprazole (dexlansoprazole), diazepam, gliclazide, (S)- lansoprazole, (R)-mephobarbital, (R)- omeprazole, omeprazole, pantoprazole, proguanil, rabeprazole, tilidine
Sensitive substrates of CYP3A	alisporivir, almorexant, alfentanil, alpha- dihydroergocryptine, aplaviroc, atorvastatin, avanafil, avapritinib, blonanserin, bosutinib, brecanavir, brigatinib, brotizolam, budesonide, buspirone, cabazitaxel, capravirine, cobimetinib, darifenacin, dasatinib, ebastine, eletriptan, eliglustat, eplerenone, everolimus, felodipine, fluticasone, grazoprevir, ibrutinib, itacitinib, ivabradine, ivacaftor, levomethadyl (LAAM), lomitapide, lovastatin, lumefantrine, lurasidone, maraviroc, midazolam, midostaurin, morphothiadin, naloxegol, neratinib, nisoldipine, perospirone, quetiapine, ridaforolimus, sildenafil, simeprevir, simvastatin, ticagrelor, tilidine, tolvaptan, triazolam, ubrogepant, ulipristal, vardenafil, venetoclax, vicriviroc, vilaprisan, voclosporin

 Table 16-10
 Sensitive CYP substrates

	5.6 Rule of exclusion criteria of analysis sets			
6	Refer	ence		

List of tables

Table 2-1	PK Parameters	
	Commercially Confidential Information	
Table 5-1	FACIT-F questions	
Table 5-2	K-BILD Response Option Weightings	
Table 5-3	Criteria leading to exclusion	

List of figures

Figure 1-1	Study design6
------------	---------------

List of abbreviations

AE	Adverse Event
AUC	Area Under the Curve
b.i.d.	bis in die/twice a day
BMI	Body Mass Index
Cmax	Maximal concentration
CSR	Clinical study report
eCRF	Electronic Case Report/Record Form
ECG	Electrocardiography
ESSDAI	EULAR Sjögren's Syndrome Disease Activity Index
ESSPRI	EULAR Sjögren's Syndrome Participant Reported Index
EudraCT	European Union Drug Regulating Authorities Clinical Trials
EULAR	European League against Rheumatism
FACIT-F	Functional Assessment of Chronic Illness Therapy-Fatigue
FAS	Full Analysis Set
FEV	Forced Expiratory Volume
FVC	Forced Vital Capacity
K-BILD	King's Brief Interstitial Lung Disease
LLOQ	lower limit of quantification
MCTD	Mixed Connective Tissue Disease
MedDRA	Medical dictionary for regulatory activities
MMRM	mixed effect model for repeated measurements
MRI	Magnetic resonance imaging
mRNA	messenger RNA (ribonucleic acid)
PD	Pharmacodynamic(s)
PhGA	Physician global assessment scale
PK	Pharmacokinetic(s)
PRO	Participant Reported Outcomes
PT	Prothrombin time
QTcF	Fridericia QT correction formula
SAE	Serious Adverse Event
SAF	Safety Analysis Set
SAP	Statistical Analysis Plan
SARS-CoV-2	Severe acute respiratory syndrome coronavirus 2
SD	standard deviation
SjS	Sjögren's Syndrome
SOC	System organ class
Tmax	Time to reach maximum concentration
ULOQ	Upper limit of quantification
WHO	World Health Organization
WoC	Withdrawal of Consent

1 Introduction

The RAP documents contain detailed information to aid the production of Statistics & Programming input into the Clinical Study Report (CSR) for trial "CMHV370A12201".

The Statistical Analysis Plan (SAP) describes the implementation of the statistical analysis planned in the protocol.

Commercially Confidential Information

1.1 Study design

This is a phase 2 randomized, participant- and investigator-blinded, placebo-controlled, multicenter, parallel group basket study to evaluate the safety, tolerability and efficacy of MHV370 in participants with moderate to severe Sjögren's Syndrome (SjS) or participants with diagnosis of Mixed Connective Tissue Disease (MCTD). In case study participants receive concomitant therapy for their underlying disease and still meet entry criteria, they will remain on this therapy provided it remains stable until the end of the study.

A total of approximately 48 participants with SjS will be randomized in a 1:1 ratio to MHV370 (200 mg b.i.d.) or placebo. A total of approximately 12 participants with MCTD will be randomized in a 1:1 ratio to MHV370 (200 mg b.i.d.) or placebo.

As shown in Figure 1-1, participants will first undergo a screening period of up to 6 weeks, followed by a treatment duration of 24 weeks and a follow-up period of 4 weeks. The total duration for each participant in the study will be up to 34 weeks.

Figure 1-1 Study design

Novartis	Confidential	Page 7 of 34
SAP		Study No. CMHV370A12201

Screening and Baseline

Participants will be assessed for ESSDAI (SjS participants) and RCS, and K-BILD (MCTD participants) as well as completing safety and other assessments to confirm RNP positivity and evaluate eligibility. Eligible participants will return for the Baseline visit on Day 1, to complete baseline assessments prior to dosing on Day 1. Some baseline assessments may be carried out on the day prior to Day 1.

Treatment

As shown from Figure 1-1, treatment period lasts for 24 weeks, from Day 1 to Week 24 (Day 169). On Day 1,

Commercially Confidential Information

Follow-up and End of Study visit (EoS)

After the last day of dosing, participants will enter a 4-week follow-up period without study drug treatment. Participants will be asked to return to the site at Week 28 for the End of Study visit. Upon competition of this visit, participants will be discharged from the study.

1.2.1 Primary estimands

The estimand is the precise description of the treatment effect and reflects strategies to address events occurring during trial conduct which could impact the interpretation of the trial results (e.g. premature discontinuation of treatment).

SjS

The primary clinical question of interest is: What is the effect of MHV370 on change in ESSDAI total score after 24 weeks of treatment in participants with moderate to severe Sjögren's Syndrome who are receiving a stable dose of a certain concomitant medication (systemic corticosteroid treatment, azathioprine, methotrexate, leflunomide,

Novartis	Confidential	Page 9 of 34
SAP		Study No. CMHV370A12201

hydroxychloroquine (HCQ) and chloroquine (CQ)), had treatment continued for the entire 24 week duration, had no dose change in certain allowed concomitant medication occurred and had no prohibited medication been taken?

The justification for the primary estimand is that wish to estimate the effect of the study drug for the full treatment duration when administered without dose changes in certain allowed concomitant medication (systemic corticosteroid treatment, azathioprine, methotrexate, leflunomide, HCQ and CQ) and without intake of prohibited medication.

The primary estimand is described by the following attributes:

- 1. Population: Participants with moderate to severe Sjögren's Syndrome receiving a stable dose of a certain concomitant medication (systemic corticosteroid treatment, azathioprine, methotrexate, leflunomide, HCQ and CQ).
- 2. Endpoint: Change from baseline in ESSDAI total score at Week 24.
- 3. Treatment of interest: the randomized treatment (investigational treatment MHV370 or placebo) with or without the allowed concomitant medication.
- 4. Handling of remaining intercurrent events:
 - Treatment discontinuations for any reason: had participants taken the assigned treatment for the entire study duration (hypothetical strategy).
 - Unforeseen change in the dose of certain allowed concomitant medication: had no change in the dose of systemic corticosteroid treatment, azathioprine, methotrexate, leflunomide, HCQ and CQ occurred (hypothetical strategy).
 - Intake of prohibited medication: had no prohibited medication been taken (hypothetical strategy).
- 5. The summary measure: Difference in mean change from baseline in ESSDAI total score at Week 24 between treatments.

MCTD

The primary clinical question of interest is: What is the effect of MHV370 on change in PhGA after 24 weeks of treatment in participants with MCTD who are receiving a stable dose of a certain concomitant medication (systemic corticosteroid treatment, azathioprine, methotrexate, leflunomide, HCQ and CQ), had treatment continued for the entire 24 week duration, had no dose change in certain allowed concomitant medication occurred and had no prohibited medication been taken?

The justification for the primary estimand is that wish to estimate the effect of the study drug for the full treatment duration when administered without dose changes in certain allowed concomitant medication (systemic corticosteroid treatment, azathioprine, methotrexate, leflunomide, HCQ and CQ) and without intake of prohibited medication.

The primary estimand is described by the following attributes:

- 1. Population: Participants with MCTD receiving a stable dose of certain concomitant medication (systemic corticosteroid treatment, azathioprine, methotrexate, leflunomide, HCQ and CQ).
- 2. Endpoint: Change from baseline in PhGA at Week 24.

Novartis	Confidential	Page 10 of 34
SAP		Study No. CMHV370A12201

- 3. Treatment of interest: the randomized treatment (investigational treatment MHV370 or placebo) with or without the allowed concomitant medication.
- 4. Handling of remaining intercurrent events:
 - Treatment discontinuations for any reason: had participants taken the assigned treatment for the entire study duration (hypothetical strategy).
 - Unforeseen change in the dose of certain allowed concomitant medication: had no change in the dose of systemic corticosteroid treatment, azathioprine, methotrexate, leflunomide, HCQ and CQ occurred (hypothetical strategy).
 - Intake of prohibited medication: had no prohibited medication been taken (hypothetical strategy).
- 5. The summary measure: Difference in mean change from baseline in PhGA at Week 24 between treatments.

2 Statistical methods

2.1 Data analysis general information

Blinded analyses using dummy treatment codes will be produced by CCI statisticians and programmers according to this SAP, using SAS version 9.4 or later (SAS Institute, Cary NC). Programs and datasets will then be provided to and run by CCI Statistician and Programmer using the true treatment codes to provide the unblinded TLFs in electronic format for discussion.

Interim analyses

One interim analysis is planned for this study, as described in Section 2.13.

Data collected up to the cut-off date will be included in the analysis. The data will include the subjects at various stages of the study. Some subjects may have full data while some may only have partial data available.

Descriptive statistics

Descriptive statistics on continuous data will include mean, standard deviation, median, minimum and maximum, while categorical data will be summarized as frequencies and percentages.

Analyses will be provided *separately* for SjS and MCTD, unless otherwise specified.

In shift tables and tables of abnormal values all unscheduled assessments are included.

Commercially Confidential Information

2.1.1 General definitions

Study treatment refers to MHV370 200 mg b.i.d or placebo.

The term '*date of first administration of study drug/treatment*' refers to the date on which the study drug/treatment was given for the first time in the CMHV370A12201 study.

The term '*date of last administration of study drug/treatment*' refers to the date on which the study drug/treatment was given for the last time in the CMHV370A12201 study.

The term '*study day*' refers to the Analysis Relative Day, Relative Start Day or Relative End Day, as applicable. Day 1 is defined as the date of first dose of study drug (MHV370 or placebo). Study day is defined as the number of days since the date of first dose of study treatment (Day 1).

Therefore, for a particular date, study day will be calculated as follows:

• for dates on or after the first administration of study treatment,

Study day = Assessment date – Date of first dose of study treatment +1

for dates prior to the date of first administration of study treatment,
 Study day = Assessment date – Date of first dose of study treatment.

The term '*baseline*' refers to the last assessment performed prior to administration of the first dose of study treatment. In case the scheduled baseline assessment value is missing, the scheduled screening value if available will be used instead.

The term '*Treatment period*' refers to the 24 weeks period from Day 1 to Week 24 (Day 169).

The term '*treatment-emergent adverse event*' refers to any adverse event (AE) started after the first dose of study treatment, or events present prior to the first dose of study treatment but increased in severity (based on preferred term (PT)).

The term '*concomitant medication*' refers to any medication (except study medication) given after the first dose of the randomized study treatment.

2.2 Analysis sets

For all analysis sets, participants will be analyzed according to the study treatment(s) received.

The safety analysis set will include all participants that received any study drug.

The **PK analysis set** will include all participants with at least one available valid (i.e. not flagged for exclusion) PK concentration measurement, who received any study drug and with no protocol deviations with impact on PK data.

The **PD** analysis set will include all participants who received study drug and have no protocol deviations with relevant impact on PD/efficacy data.

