 MCTD: To evaluate the efficacy of MHV370 based on change from baseline in the patient reported outcome on lung function. 	• MCTD: Change from baseline in King's Brief Interstitial Lung Diseas (K-BILD) over time up to week 24	
 MCTD: To evaluate the efficacy of MHV370 based on change from baseline in Raynaud's Condition Score (RCS) over time up to Week 24 	• MCTD: Change from baseline in RCS over time up to Week 24	
Exploratory objective(s)	Endpoint(s) for exploratory objective(s)	

Objective(s)

Endpoint(s)

Commercially Confidential Information

2.1 **Primary estimands**

The estimand is the precise description of the treatment effect and reflects strategies to address events occurring during trial conduct which could impact the interpretation of the trial results (e.g. premature discontinuation of treatment).

SjS

The primary clinical question of interest is: What is the effect of MHV370 on change in ESSDAI total score after 24 weeks of treatment in patients with moderate to severe Sjögren's Syndrome who are receiving a stable dose of certain concomitant medication (systemic corticosteroid treatment, azathioprine, methotrexate, leflunomide, hydroxychloroquine (HCQ) and chloroquine (CQ)), had treatment continued for the entire 24 week duration, had no dose change in certain allowed concomitant medication occurred and had no prohibited medication been taken?

The justification for the primary estimand is that wish to estimate the effect of the study drug for the full treatment duration when administered without dose changes in certain allowed concomitant medication (systemic corticosteroid treatment, azathioprine, methotrexate, leflunomide, HCQ and CQ) and without intake of prohibited medication.

The primary estimand is described by the following attributes:

- 1. Population: Patients with moderate to severe Sjögren's Syndrome receiving a stable dose of certain concomitant medication (systemic corticosteroid treatment, azathioprine, methotrexate, leflunomide, HCQ and CQ). Further details about the population are provided in Section 5.
- 2. Endpoint: Change from baseline in ESSDAI total score at Week 24.
- 3. Treatment of interest: the randomized treatment (investigational treatment MHV370 or placebo) with or without the allowed concomitant medication.
- 4. Handling of remaining intercurrent events:
 - Treatment discontinuations for any reason: had participants taken the assigned treatment for the entire study duration (hypothetical strategy).

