12.1 Analysis sets

For all analysis sets, participants will be analyzed according to the study treatment(s) received.

The safety analysis set will include all participants that received any study drug.

The PK analysis set will include all participants with at least one available valid (i.e. not flagged for exclusion) PK concentration measurement, who received MHV370 and with no protocol deviations with impact on PK data.

The PD analysis set will include all participants who received any study drug and have no protocol deviations with relevant impact on PD/efficacy data.

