12.4 Analysis supporting primary objectives

The PD analysis set will be used.

SjS

The primary objective is to assess the efficacy of MHV370 based on change from baseline in ESSDAI at Week 24. The statistical analysis model will include data on the ESSDAI from all time points at which it was recorded (Baseline, Week 4, Week 8, Week 12, Week 20, Week 24) but the primary comparison is made for Week 24.

MCTD

The primary objective is to assess the efficacy of MHV370 based on change from baseline in Physician Global Assessment (PhGA) at Week 24. The statistical analysis model will include data on the PhGA from all time points at which it was recorded (baseline, Week 4, Week 8, Week 12, Week 20, Week 24) but the primary comparison is made for Week 24.

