2.5 Analysis supporting primary objective(s)

All participants within the PD analysis set will be included for the primary analyses.

2.5.1 **Primary endpoint(s)**

SjS

The primary endpoint is the change from baseline in ESSDAI total score at Week 24, defined as the Week 24 visit ESSDAI total score minus the baseline ESSDAI total score. A negative change indicates an improvement of disease activity. Details for the derivation of ESSDAI total score can be found in Appendix 5.4.1.1.

The ESSDAI score for SjS participants will be listed by treatment group, participant and visit/time. Descriptive statistics (raw and change from baseline) will be provided by treatment group and visit/time. Graphical methods, such as spaghetti plots up to Week 24, may be employed by treatment and visit/time. In addition, bar plots will be used to visualize (1) the contribution of the individual ESSDAI domains to the estimated change from baseline in the total ESSDAI score by treatment group and visit/time and (2) the difference in the contribution of the individual ESSDAI domains to the estimated change from baseline in the total ESSDAI score by treatment groups by visit/time.

MCTD

The primary endpoint is the change from baseline in PhGA (ranging from "no disease activity" (0) to "maximal disease activity" (100)) after 24 weeks of treatment. It is defined as the Week 24 visit PhGA value minus the baseline PhGA value. A negative change indicates an improvement in disease activity. The PhGA score for MCTD participants, will be listed by treatment group, participant and visit/time. Descriptive statistics (raw and change from baseline) will be provided by treatment group and visit/time. Graphical methods, such as spaghetti plots up to Week 24, may be employed by treatment and visit/time.

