2.5.3 Handling of intercurrent events

SjS and MCTD

The primary analysis will account for different intercurrent events as explained in the following:

- 1. Treatment discontinuation: Data from participants who have discontinued treatment early will be regarded as missing after the treatment discontinuation. Data from participants who have temporarily discontinued treatment (defined as missing more than two consecutive doses) will be regarded as missing during the temporary treatment discontinuation.
- 2. Any change in the dose of certain allowed concomitant mediation (systemic corticosteroid treatment [bethamethasone, prednisone, prednisolone, triamcinolone, methylprednisolone, dexamethasone, hydrocortisone, cortisone, ethamethasoneb], azathioprine, methotrexate, leflunomide, HCQ and CQ). Data after change in the dose of allowed concomitant medication will be regarded as missing (identified with OTH12 protocol deviation code).
- 3. Intake of prohibited medication: Data after intake of prohibited medication will be regarded as missing (identified with COMD01 protocol deviation code).

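### The primary efficacy set drops participants for efficacy-relevant protocol deviations, with no visible limit to pre-randomization ones, and groups by treatment received, which does not match the estimand

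*SAP*

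**What the plan says.** Protocol 12.1 defines the PD analysis set as participants "who received any study drug and have no protocol deviations with relevant impact on PD/efficacy data". SAP 2.2 is nearly identical: dosed participants must "have no protocol deviations with relevant impact on PD/efficacy data". For every analysis set, "participants will be analyzed according to the study treatment(s) received".

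Protocol 12.4 assigns this set to the primary analysis for both diseases ("The PD analysis set will be used"). SAP 2.5 agrees: "All participants within the PD analysis set will be included for the primary analyses". SAP 2.6 names the same set for the secondary analyses.

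The estimand (Protocol 2.1, SAP 1.2.1) is framed differently: "Treatment of interest: the randomized treatment (investigational treatment MHV370 or placebo"). Treatment discontinuation, dose changes in listed background drugs and prohibited medication all get a hypothetical strategy. SAP 2.5.3 implements this at the level of data, not of participants. For dose changes: "Data after change in the dose of allowed concomitant medication will be regarded as missing (identified with OTH12 protocol deviation code"). Prohibited medication is handled the same way under code COMD01. Protocol 12.4.6 keeps the same target population for the supplementary analysis and uses the data from participants with these events.

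**The concern.** A set that removes participants for efficacy-relevant deviations is in effect a per-protocol set. If those deviations can arise after randomization, the remaining groups are no longer the randomized groups, and the population is no longer that of the estimand.

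Exclusion could be related to outcome. SAP 2.5.3 covers "Any change in the dose of certain allowed concomitant mediation (systemic corticosteroid treatment" among other drugs, and Protocol 6.2.3 allows high-dose steroid as rescue when systemic disease flares severely. A participant who is doing badly may therefore be the one who acquires a deviation code. For prohibited medication the link is weaker: Protocol 6.2.3 accepts that a Table 6-3 drug may be needed as rescue, but no immunosuppressant row of that table is visible.

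There is also a point to confirm, which is not a demonstrated conflict. SAP 2.5.3 identifies two intercurrent events by protocol deviation codes. Read literally, one event could trigger both the rule that removes later data and the rule that removes the participant. The visible text does not say which prevails.

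Grouping by treatment received is a second departure from the estimand. It changes results only if someone receives the wrong treatment.

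**Working it through.** **The plan's own figure.** SAP 3.1 gives SD 5.1, 20 per arm and a true difference of 3.5; SAP 2.5.2 gives one-sided 10% significance and an estimate of at least 2 points.

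- SE = 5.1 × √(2/20) = 1.61.
- Significance threshold, normal approximation: 1.2816 × 1.613 = 2.07. This exceeds 2, so significance is the tighter criterion on average.
- Chance of meeting both criteria: 81.3% (normal approximation) or 79.8% (simulated t-test, 38 df). At zero difference: 10.0% or 9.3%.

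The stated values of about 80% and about 10% reproduce. The sample size is not in dispute.

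**What exclusion does, compared with the SAP 2.5.3 rule.** The documents give no deviation rates, so the following inputs are assumptions:

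- Changes from baseline are normal with SD 5.1, and the correlation ρ between any two visits is 0.5 or 0.7.
- The MHV370 effect grows linearly to 3.5 points at Week 24.
- An event follows the Week w visit if the change at that visit is among the worst q of placebo, with q = 8% or 17%. For scale, the plan's allowance for loss is 8/48 = 16.7%. The trigger value is the same in both arms.
- A share s of event participants is excluded. The rest stay in, with later visits missing at random.
- The baseline covariate is left out.

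With a = z(1 − q) on placebo and a′ = a + 3.5 × (w/24)/5.1 on MHV370, each arm's Week 24 mean moves towards improvement by

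ρ × 5.1 × s × φ(a) / [1 − s × (1 − Φ(a))],

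using a′ for MHV370. The estimated benefit shrinks by the placebo term minus the MHV370 term.

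Worked case, w = 12, ρ = 0.5, q = 17%, s = 1:

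- Placebo: a = 0.954, φ = 0.2531; 0.5 × 5.1 × 0.2531/0.83 = 0.78.
- MHV370: a′ = 0.954 + 0.343 = 1.297, φ = 0.1720, upper tail 0.0973; 0.5 × 5.1 × 0.1720/0.9027 = 0.49.
- Shrinkage: 0.29 points.

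Shrinkage in points with all event participants excluded (s = 1):

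| Event after | ρ 0.5, q 8% | ρ 0.5, q 17% | ρ 0.7, q 8% | ρ 0.7, q 17% |
|---|---|---|---|---|
| Week 4 | 0.07 | 0.11 | 0.10 | 0.15 |
| Week 8 | 0.13 | 0.20 | 0.18 | 0.29 |
| Week 12 | 0.18 | 0.29 | 0.26 | 0.41 |
| Week 20 | 0.26 | 0.44 | 0.37 | 0.61 |

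With half excluded (s = 0.5) the range is 0.03 to 0.26. There is no shift if nobody is excluded, if the event precedes Week 4 (the participant then has no usable post-baseline data under either rule), or if the true difference is zero.

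**Effect on the decision.** The Week 12 row takes the estimate from 3.50 to between 3.32 and 3.09, a shift of 0.18/1.61 = 0.11 to 0.41/1.61 = 0.25 standard errors. The simulated chance of meeting both criteria is 79.8% at 3.50, 76.5% at 3.32 and 72.0% at 3.09. This counts the shift only, not the smaller number analysed.

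**Events in one arm only, as bounds.** With s = 1, exclusions on placebo alone shrink the benefit by 0.41 to 1.09 points. Exclusions on MHV370 alone inflate it by 0.15 to 0.94 points if the true difference is 3.5, and by 0.41 to 1.09 if it is zero. So the direction is not fixed.

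**The case against.** The strongest objection is that the operative rule is hidden. SAP 5.6 announces Table 5-3 with the exclusion criteria, but its rows are not shown. SAP 2.5.5 and 2.5.6 are redacted, and a full analysis set appears in the SAP abbreviation list without being used in the visible text. An all-treated analysis may therefore exist. The more coherent reading of SAP 2.5.3 and Protocol 12.4.6 is also that participants with OTH12 or COMD01 stay in, because those provisions would otherwise have nothing to act on. On that reading every non-zero figure above disappears. It is also unclear which code a newly started rescue steroid would receive. Wrong-treatment cases should be rare with kits assigned by IRT, and under a common trigger the shift is towards no effect and adds no false positives.

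Most of this stands as a limit on size. The two-code overlap must be confirmed, not asserted, and nothing hidden counts as an omission. It does not remove the main point. The visible text of both documents makes the PD set primary. Exempting the two codes would still leave any other post-randomization deviation that the table allows, and the grouping by treatment received. Nor is a common trigger in both arms guaranteed.

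It is also fair that changing only the SAP leaves Protocol 12.1 and 12.4 naming a different set. SAP section 4 exists to record such a departure.

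**Conclusion.** The concern holds and should be fixed; confidence is medium. As written, the primary analysis set permits outcome-related exclusion after randomization and groups participants by a treatment definition other than the estimand's. The actual bias cannot be derived from the documents and may be nil. Under the assumptions shown, it is at most 0.61 points with a common trigger in both arms, and up to about 1.1 points in either direction if events fall in one arm alone, against a planned difference of 3.5. The numerical illustration covers only exclusion of participants with intercurrent events in the SjS cohort. The set definition applies equally to the MCTD primary analysis.

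**What to change.** In SAP 2.2, 2.5 and 2.6, run the primary, secondary and supplementary efficacy analyses on all randomized participants who received at least one dose, analysed as randomized. Handle OTH12 and COMD01 only through the SAP 2.5.3 data rules, and ignore those events in the supplementary analysis as Protocol 12.4.6 intends. Confirm in Table 5-3 that neither code removes a participant. Keep the PD set for biomarker work or as a sensitivity analysis. Record the change in SAP section 4, which now reports none.

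The cost is SAP wording and a little extra analysis, with no new data. The estimate may move either way. The SAP alone is enough to make the change. If Protocol 12.1 and 12.4 are aligned as well, Protocol 14.1 requires a written amendment approved by the sponsor, the IRB/IEC and, where required, health authorities.
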